At MUSC, [name] and the brain stimulation division have conducted three focused studies examining the safety, feasibility, and effectiveness of taVNS in adults. They found that during taVNS, participants showed minor but statistically significant immediate heart rate decreases followed by a modest sympathetic rebound upon termination of stimulation. The group developed and conducted a concurrent taVNS/fMRI trial to determine the neurobiological effect of taVNS. Findings from the taVNS/fMRI trial demonstrated that the neurobiological effect of taVNS mimics that of cervically implanted VNS and targets several cortical and subcortical vagus afferent pathway targets. It additionally suggested that taVNS for short time periods activates the vagus nerve (10-25Hz, average 1.8mA). The group saw no minor or major adverse events during the treatment sessions and no spontaneously reported event following termination of the trial. No rapidly accelerated or sustained drops in HR were seen during the one-minute taVNS stimulation periods. Minor, temporary, and light redness was seen at the sight of stimulation but disappeared within five minutes of stimulation completion. A follow-up study determined that the optimal parameter to modulate the parasympathetic response activated via taVNS was 500 μ s pulse width, 10Hz for 60s duration (10).

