[name], Ph.D, obtained his doctorate under [name], and has extensive experience and background in clinical TMS and taVNS, especially in the development of novel protocols for neurological disorders. His thesis work involves systematic elucidation of the dose response of taVNS on heart rate, use of heart rate as a biomarker of taVNS effect, and the use of taVNS with fMRI in determining pathways and regions affected by taVNS in adults. He determined that the 'on' pulse heart rate change was a mean of -3 beats per minute (bpm) while the 'off' pulse heart rate change was +6 bpm. Although these are statistically significant and measurable changes, they are physiologically insignificant. Nevertheless, this will be an important biomarker for infants, but is not expected to result in safety concerns. [name] careful and thorough studies lay the safety and efficacy groundwork for the current proposal.

D. RESEARCH DESIGN AND METHODS (including data analysis)

Due to the novelty of these studies, [name] will be present for each taVNS-paired feeding session conducted in the first participants, and as needed thereafter. [name] and or [name] will monitor taVNS effects. If any adverse events are noticed which are not described in the consent or are serious, we will inform the IRB before continuing with the next enrolled subject. Importantly, all of these methods have been done before, and published by our and other groups in adults, and we believe these extra precautions will assure the safety and well-being of any participants enrolled.

taVNS-paired feeding to enhance feeding behavior in neonates

Screening

Prospective participants will be identified by the PI ([name]) at the MUSC neonatal intensive care units (Level II and III), and checked for potential inclusion (please see the uploaded taVNS screening form). [name], and other clinical OTs based in the nursery may also mention the study to parents and refer them to [name] if they are interested in participating.

Participants

Inclusion criteria:

Infants must be clinically stable, on minimal respiratory support (nasal cannula, or room air), in discussions about Gtube placement for poor po feeding and are currently greater than or equal to 39 weeks post-menstrual age and

- 1) If born premature have been working on oral feeding for 30days;
or

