Up to 40 preterm/HIE neonates will be enrolled in this prospective, open-label safety and feasibility trial, with a dose response. The experimental paradigm consists of 2 to 3 weeks of once or twice daily taVNS-paired feeding.

Our control group was investigated by Drs. [name] and [name] at MUSC, who have researched all infants failing feeding and getting Gastrostomy tubes in our nurseries over the past 5 years. We can compare our data to this historical group at our own institution.

All consented participants will receive the active stimulation condition.

taVNS Stimulation (in Detail)

After obtaining consent and describing this procedure to the parents and all members of the baby's care team, we will first, with a 500 μ s, 25Hz pulse, gradually increase the intensity of the TENS unit until the baby can first feel something in their ear. We will use the facial expression change and fidgety movements to determine when the infants feel the stimulation. This intensity will be recorded as the perceptual sensory threshold. The stimulation intensity we will use for this study on taVNS-paired feeding is a small decrement from the perceptual sensory threshold for each infant (-0.1mA), a point at which they should not react to the stimulation. We will retest the sensory threshold before every session.

Determination of Perceptual Threshold

1. Electrode clip will be placed on the left tragus in an enrolled infant at rest. Starting at 0.2mA at 25Hz, we will deliver 5 seconds of pulses, and increase by 0.1mA until the perceptual threshold is achieved by observation of the infant's facial expression, fidgety movements, or NIPPS score. This will be termed the perceptual threshold.
2. We will then deliver this level of microcurrent while the infant is feeding on the first day to determine if the perceptual threshold changes with feeding. Current will then be held constant while pulse width and frequency will be set at 500us and 25Hz, respectively.

3. Finally, we will decrease the microcurrent by 0.1mA *below the perceptual threshold* and administer this taVNS treatment during the feeding and deliver this only while the infant is actively sucking from the bottle.
4. The total duration of this 'on-and-off' taVNS stimulation treatment will continue for 30 minutes or the duration of the feed.
5. We may manually trigger the taVNS stimulation or place a gel EMG electrode over the temporomandibular joint area to trigger the taVNS impulse.

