For safety we will compare HR changes from baseline to during taVNS within subjects. We will compare treatment before and after the taVNS-paired feeding treatment for the rate of feeding volume increase, and days to full po feeds. We will use repeated measures ANOVA to analyze repeated measures such as HR over 5 minutes and mean daily feeding volumes in 7-10 day epochs. We will analyze the number of infants who reach full feeds vs requiring G-tube during taVNS-paired feeding, between once and twice daily stimulation by Chi-squared. We will assess differences in kurtosis parameters from pre-to post taVNS scans by paired t-test, and between those that reach full oral feeds vs those that require a Gtube by unpaired t-test.

Estimated Difficulties, Limitations and Time Frames

Estimated Difficulties. Many of the initial parameters for taVNS in humans, such as frequency and pulse width, were accomplished in trials at MUSC by [name] et al. that were approved by the IRB. In one sense, we will be shrinking many of the components into miniature form to deliver stimulation to neonates and infants. In spite of the clear differences in size and skin between the neonatal and adult ear, the custom electrodes have been fitted to several different weights of infants (2.5-4.0 kg).

Limitations. We will not be delivering a SHAM stimulation paradigm (electrodes and Digitizer with appearance of taVNs treatment without actual current). Our goal is to determine safety and feasibility of active treatment with a dose response in order to investigate whether this should be administered in a larger randomized control trial. In this respect, the comparison we lose in not having a SHAM stimulation is offset by the validation we will receive in the safety and feasibility of active treatment. We will compare our overall results with characteristics of infants who required a Gtube from [name] and [name]'s publications.

Estimated Time Frames. The duration of the study will likely be ~4 years, with 2 years of active enrollment and 18 months of follow-up.

E. PROTECTION OF HUMAN SUBJECTS

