2. ADEQUACY OF PROTECTION AGAINST RISKS

a. Recruitment and Informed Consent

This information is listed on the eIRB website.

b. Protection against Risk

The following risks are present with this study: Risk of skin irritation, risk of discomfort, risk of slightly decreased heart rate, and risk of loss of confidentiality.

Risk of skin irritation: we will monitor the skin on the inner aspect of the left ear before and after each session, and will switch to the right ear if redness is present, and decrease the stimulation if redness persists.

Risk of discomfort: We expect to be able to use the pain ratings scales to identify the perception of tingling versus pain with taVNS in these infants. We will use facial expression change, fidgety movements and infant behavioral discomfort using our standard neonatal pain scale (NIPS) with the bedside nurse at the start and after 5 minutes of taVNS, at 10 minutes and at the end of treatment. We will protect against the risk of discomfort by close monitoring and by the determination of perceptual threshold using the protocol outlined above.

We will hold the treatment for a NIPS score of >3 , until discomfort subsides, and resume at a lower stimulus level if this level of discomfort recurs. We do not expect the infant to cry at this level, but show discomfort in brow furrowing, grimace, etc. Feeding is generally comforting for infants, and we expect to see minimal pain response to treatment. Infants are fed sidelying in the nursery. We will position the baby so that the left ear is facing up, and we can monitor the site and pain without disturbing the feeding process unduly.

Risk of slightly decreased heart rate: we will monitor HR, respiratory rate and oxygen saturation continually during the feeding to monitor these physiologic responses to taVNS-paired feeding. The infants' vital signs are constantly monitored as standard of care while in the nursery. We will print out values at baseline, and changes with feeding and taVNS-paired feeding. Normal heart rate is 120-170 beats per minute in preterm infants feeding, and 110-140 bpm in term HIE infants. As HR usually accelerates with motor activity of feeding, we do not expect significant bradycardic HR changes during the 'on' pulse. However, if the HR decreases to <100 bpm during 'on' pulse, or if HR rebound is >190 bpm during 'off' pulse, we will hold treatment and start again at a lower stimulation level.

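### The heart-rate safety analysis does not separate stimulation-on from stimulation-off time, although the protocol expects opposite effects in the two

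*Combined protocol and SAP*

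**What the plan says.** The Data Analysis part of section D gives the HR safety comparison in one sentence: "For safety we will compare HR changes from baseline to during taVNS within subjects". The method follows, repeated measures ANOVA for "repeated measures such as HR over 5 minutes". It defines no baseline, on or off phase, sampling interval, or lowest or highest value.

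Other sections describe an effect that depends on phase:

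- Section B (Background and Significance) reports from the adult studies "immediate heart rate decreases followed by a modest sympathetic rebound upon termination of stimulation".
- Section C (Preliminary Studies) gives the adult figures as "on' pulse heart rate change was a mean of -3 beats per minute (bpm) while the 'off' pulse heart rate change was +6 bpm". The bradycardia paragraph under Potential Risks (section E.1.c) repeats −3 and +6 bpm.
- Under Determination of Perceptual Threshold (section D): "The total duration of this 'on-and-off' taVNS stimulation treatment will continue for 30 minutes or the duration of the feed". The text after it says that stimulation and a timer start with sucking, stop when sucking stops, and restart with it.
- Section E.2.b (Protection against Risk) holds treatment "if the HR decreases to <100 bpm during 'on' pulse, or if HR rebound is >190 bpm during 'off' pulse". It also plans printed values at baseline, with feeding, and with stimulated feeding, but not on against off.

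**The concern.** The protocol expects a fall while stimulation is on and a larger rise once it stops, and it watches for the two separately at the bedside. The analysis does not carry this distinction through. A summary over a period holding both phases is a weighted mix of a fall and a rise, and the weight is the infant's sucking share. That share should rise as feeding improves, so a pooled HR change could move with feeding performance, which is the trial's efficacy outcome. It could also differ between good and poor feeders for reasons unrelated to how the heart responds.

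HR is the only safety measure for which Data Analysis states a comparison, and safety is a main purpose of the trial. What is at stake is whether the reported result can show how infants respond in each phase.

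**Working it through.** **1. Is there a figure to reproduce?** No. The protocol gives no SD, power or sample-size calculation for HR.

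**2. Inputs.** On effect −3 bpm and off effect +6 bpm (section C, adult data). Up to 40 infants, all on active stimulation (Study Design). Automatic shut-off of the Soterix unit after 120 seconds (section E.1.c). The share of time on, f, is not given, so it is assumed to lie between 0.3 and 0.9.

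**3. Reading A: the comparison covers the whole session.** The expected change is the time-weighted mean of the two effects.

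- If +6 is measured from baseline: −3f + 6(1 − f) = 6 − 9f. This is zero at f = 6/9 = 0.67.
- If +6 is measured from the on level, the off phase lies 3 bpm above baseline: −3f + 3(1 − f) = 3 − 6f. This is zero at f = 3/6 = 0.5.

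| f | 6 − 9f (bpm) | 3 − 6f (bpm) |
|---|---|---|
| 0.3 | +3.3 | +1.2 |
| 0.4 | +2.4 | +0.6 |
| 0.5 | +1.5 | 0 |
| 0.6 | +0.6 | −0.6 |
| 2/3 | 0 | −1.0 |
| 0.8 | −1.2 | −1.8 |
| 0.9 | −2.1 | −2.4 |

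Exact cancellation needs one particular f. Elsewhere the result is diluted, and its sign depends on f.

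**4. Can one on-run fill five minutes?** Not on the Soterix unit. If a 300-second window held a single 120-second run and was otherwise off, the mean would be (120 × −3 + 180 × 6)/300 = 720/300 = +2.4 bpm. The fall would appear as a rise.

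**5. Reading B: the comparison covers on-time only.** Then f = 1, both formulas give −3 bpm, and nothing cancels. But no off-phase value enters the analysis, so the rebound, which is the larger stated effect and has its own hold limit, is not analysed.

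**6. Effect of feeding.** Section E.2.b says that feeding usually raises HR but gives no size. Call the rise g and suppose that it applies throughout the feed, with baseline at rest. The pooled change becomes 6 − 9f + g, with its zero at f = (6 + g)/9, or 3 − 6f + g, with its zero at f = (3 + g)/6. Both zeros pass f = 1 once g exceeds 3 bpm, so cancellation to zero is not assured. The on-phase change from rest is then −3 + g, which is also no longer a fall once g reaches 3. An undefined baseline therefore matters even when the phases are split.

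**7. Illustrative power.** Paired test, normal approximation, n = 40, two-sided 0.05, feeding effect ignored, with the SD of within-infant change assumed at 5, 8 or 10 bpm and equal for pooled and separate means. Power ≈ Φ(|mean| × √40/SD − 1.96). For the on-phase at SD 5: 3 × 6.325/5 − 1.96 = 1.83, which gives 97%.

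| Quantity (6 − 9f version) | SD 5 | SD 8 | SD 10 |
|---|---|---|---|
| On-phase alone, −3 bpm | 97% | 66% | 48% |
| Off-phase alone, +6 bpm | >99% | >99% | 97% |
| Pooled, f = 0.5, +1.5 bpm | 48% | 22% | 16% |
| Pooled, f = 2/3, 0 bpm | 5% | 5% | 5% |

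**The case against.** A reader might infer that the plan averages HR over five minutes of clock time, so that a real effect will average to zero. The documents do not support this. The sentence implies several HR readings across the window; it uses the word mean for feeding volumes and not for HR. The session timer runs only while stimulation is on, so the five minutes, like the period called during taVNS, could be accumulated on-time. Pooling is one reading of a silent text.

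The figures are also soft. They are adult means; the infant pilot is credited with the same values but no separate data are shown. The protocol calls them physiologically insignificant and expects no safety concern from them.

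A reader might also infer that harmful dips or peaks would go unseen. That does not follow. Vital signs are monitored continuously, bradycardia is defined over 5 seconds (Safety Monitoring, section D), and the hold rule distinguishes on from off. The number of treatments held for HR goes to the IRB, and the safety committee discusses data after 5 and after 10 infants (section E.5).

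Finally, splitting by phase is not a clean remedy by itself. Stimulation is on when the infant sucks, so on-phase change from baseline mixes stimulation with feeding.

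All of this stands, and it limits the point to the reported analysis. It does not remove the point. On one reading the rebound is mixed with the fall, and on the other it is left out.

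**Conclusion.** The point holds as a gap in specification: the HR safety analysis does not distinguish on from off time, and neither natural reading of it gives a usable result for both phases. Under the whole-session reading, the expected change runs from +3.3 to −2.1 bpm (6 − 9f), or from +1.2 to −2.4 bpm (3 − 6f), as f goes from 0.3 to 0.9. These sizes rest on adult figures, an assumed f and no feeding effect; the power figures rest also on assumed SDs. They show how the result depends on sucking share and do not predict it. Under the on-time reading, the on effect is kept and the rebound has no planned analysis. Bedside detection is not at fault. This is a cheap improvement, and no flaw in safety monitoring has been shown.

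**What to change.** In Data Analysis:

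- Define baseline: when it is taken, for how long, and whether at rest.
- Label each HR value on or off from the stimulation timer or EMG trigger, and analyse phase as a within-subject factor.
- Report, per session, mean and lowest HR in on phases and mean and highest HR in off phases. Extremes are needed because brief events barely move a mean: a drop from 120 to 79 bpm for 5 seconds shifts a 300-second mean by 41 × 5/300 = 0.7 bpm.
- Compare each with baseline and with the feeding values already planned in section E.2.b, taken here to be feeding without stimulation. This reduces the confounding with sucking but does not remove it, because off phases are also sucking pauses.
- Report by phase the number of sessions crossing each HR limit that the protocol already states. No limit or hold rule changes.

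The cost is time-stamping the triggers against the ECG, including when triggering is manual; storing the trace if it is now only displayed or printed; and more data handling per session. No added procedure for the infant is needed.

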**Medical University of South Carolina
Protocol**

PI Name: [name]

Co-PI: [name]

Study Title: Noninvasive Brain Stimulation to Improve Oromotor Function In Neonates

Once protocol is complete, save it as a Word document. Go back to the IRB application and upload the protocol.

TABLE OF CONTENTS – *Prepare a table of contents based on the following outline, including page numbers, and insert here.*

Specific Aims.....	2
Background and Significance.....	2
Preliminary Studies.....	3
Research Design and Study Methods.....	4
Protection of Human Subjects.....	8
References.....	15
Facilities.....	18

A. SPECIFIC AIMS

Preterm infants and term infants who suffer hypoxic ischemic encephalopathy (HIE) are at high risk for motor problems, which primarily manifest as feeding delays during their neonatal hospital admission. Oromotor dyscoordination is very common in both groups of infants, and typically takes 3-6 weeks of working on oral feedings in the hospital before the infant may take enough breast milk or formula to sustain adequate growth for discharge. Occupational therapy usually works with infants once a day to ensure that the feeding particulars, such as nipple choice, frequency of oral feeding, do not tax infant physiology too greatly and to guide learning this motor skill. Feeding difficulty is the primary reason for delayed discharge of preterm or HIE infants. Many of these infants will not be able to master this motor skill before term age (40-42 weeks gestation) and will receive a gastrostomy tube (G-tube) for direct gastric feeding, in order that they may finally be discharged from the hospital to home. Over the past 5 years in our MUSC NICU (2012-2016), we have placed an average of 40 G-tubes per year. This procedure requires general anesthesia for both insertion and eventual take down, and leaves scars in the epigastric area. The G-tube also reinforces the parental perception that their child is not normal and that he or she has a more limited developmental potential than a 'normal' child.

Even with significant brain injury, we know that neuroplasticity in infants may lead to improved, and even near normal outcomes. This neuroplasticity involves stimulating neurogenesis and reparative inter-neuronal connections to improve motor skills in neonatal animal models and in adults after stroke. In addition, we know that rehabilitative training may be enhanced by brain stimulation using a variety of modalities.

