Feeding in neonates involves a sequence of sucking, swallowing, and breathing that requires coordination of the face, head, and neck muscles with the myelinated vagal regulation of the bronchi and the heart (11). In preterm neonates, the muscles needed to feed are underdeveloped, resulting in the need for OT rehabilitation to 'learn' feeding patterns. Preterm neonates' inability to feed effectively is the primary reason for prolonged hospital stays (12). In neonates with HIE, development of cortex and basal ganglia is interrupted, and depending on the severity, normal developmental plasticity is hindered, further contributing to their inability to feed (13). Both types of feeding difficulties involve complex motor learning, which requires integration of sensory and motor pathways. Treating oromotor difficulties during the learned task of feeding with noninvasive brain stimulation that promotes plasticity, poses a highly novel application of taVNS. Our major premise is that in babies at high risk for motor problems, simultaneously delivered brain stimulation via taVNS will boost motor cortical plasticity involved in a learned feeding task, leading to better feeding.

This protocol has 2 specific aims that will be investigated:

Specific Aim 1: Improved Motor Learning - We aim to investigate whether pairing taVNS with rehabilitation training of feeding behavior in preterm and HIE neonates will enhance and accelerate the learning of effective feeding behavior in a dose responsive manner. We call this treatment "taVNS-paired feeding." The primary outcome measures of taVNS-paired feeding will be daily oral milk feeding volume changes from before to during treatment, and number of infants reaching full oral feeds

between once and twice daily taVNS-paired feeding, duration to full feeds, as well as general motor functional impairment as measured by [name] Test of Early infant motor Performance (STEP). Our hypothesis is that taVNS-paired feeding for preterm neonates is feasible, safe and effective at reducing length of stay solely for feeding reasons, compared to historical controls. As part of our safety investigations with separate funding, we may perform taVNS during a clinical modified barium swallow study with pediatric speech language pathologists performing the study and compare 10 swallows with stimulation on and off to determine if taVNS affects swallowing parameters.

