- 2) If term Infant with significant medical issues that have precluded oral feeding, such as hypoxic ischemic encephalopathy (HIE), have been working on oral feeding for 14days.

Exclusion criteria:

- 1) Unstable infants or those requiring respiratory support involving positive pressure.
- 2) Major unrepaired congenital anomalies
- 3) Anomalies/conditions that limit feeding volumes
- 4) Cardiomyopathy
- 5) Repeated episodes of autonomic instability (apnea or bradycardia) which are not self-resolving *

*Preterm infants commonly have short periods of shallow or absent breathing or lower heart rate termed apnea and bradycardia, respectively, and most are being treated for these physiologic manifestations of prematurity with caffeine, an effective central stimulant. Infants are on cardiorespiratory monitors through the nursery stay to capture events, many of which are self-resolving. Infants who require repeated episodes of tactile stimulation to come out of these events are defined as *unstable*.

Neonates who are beginning oral feeds after medical treatment for critical illnesses, such as HIE brain injury, will be included as these neonates represent a population in which taVNS-paired feeding could present the largest success in overcoming impaired brain development. Congenital syndromes may be included if the infants do not have major, unrepaired anomalies or anomalies that limit feeding volumes.

Written informed consent will be obtained from the mother if available and if she has custody or decision making authority for the participant, otherwise a parent or legal guardian, prior to participation in the experimental paradigm. Department of Social services may have custody of infant but require the parent or foster parent to consent for all medical procedures.

Electronic Consent will be used for situations when the parent (or Legally Authorized Representative) is at another hospital and cannot travel to MUSC to provide consent in person. We will use the approved REDcap system to obtain consent. [name] or other approved study personnel will go over the entire consent document on the phone with the parent to ensure comprehension and to confirm identity. Parent will be given a copy of the completed, signed consent form in person or by email or fax.

Study Design

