1. RISKS TO THE SUBJECTS

The human subjects involved in this research will be preterm neonates or infants with critical illnesses that preclude oral feeding, such as HIE. Inclusion criteria involves 2 main groups. The first is comprised of typical pre-term, high risk neonates who are in the convalescent near and post-term period and learning to po feed. The second is comprised of neonates that present after severe medical illnesses or brain injury. In both cases, the infants can only be enrolled if they are stable, not making progress with OT training, and are in discussion for Gtube placement. Participants will be excluded if they have major unrepairs congenital abnormalities that limit volume of feeds, cardiomyopathy, significant autonomic instability, such as repetitive, unresolved bradycardia or apnea, or use a continuous positive airway pressure (CPAP) device or other form of high respiratory support preventing them from breathing without assistance.

Targeted/Planned Enrollment Table

Total Planned Enrollment: 40 babies (active)

TARGETED/PLANNED ENROLLMENT: Number of Subjects receiving active taVNS			
Ethnic Category	Sex/Gender		
	Females	Males	Total
Hispanic or Latino	4	5	9
Not Hispanic or Latino	15	16	31
Ethnic Category: Total of All Subjects*			

Racial Categories			
American Indian/Alaska Native			
Asian			
Native Hawaiian or Other Pacific Islander			
Black or African American	8	7	15
White	12	13	25
Racial Categories: Total of All Subjects*	20	20	40

*The “Ethnic Category: Total of All Subjects” must be equal to the “Racial Categories: Total of All Subjects”.

Volunteers of all ethnicities and racial categories will be accepted into this study protocol. No preference will be given based on race, gender or ethnicity. No vulnerable populations or special classes of subjects will be considered for participation.

b. Sources of Materials

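### The epoch-mean analysis of feeding volume counts any rise already under way as a taVNS effect; the planned rate comparison should decide instead, and needs a model

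*Combined protocol and SAP*

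**What the plan says.** Specific Aim 1 (section A) lists "daily oral milk feeding volume changes from before to during treatment" among the primary outcome measures. Data Analysis (section D) has two statements on volume. The first is a before/after comparison "for the rate of feeding volume increase, and days to full po feeds", with no model named. The second applies repeated measures ANOVA to "mean daily feeding volumes in 7-10 day epochs". Neither is said to carry the conclusion, and no pre-treatment window is defined.

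Study Design gives active stimulation to everyone, up to 40 infants, for "2 to 3 weeks of once or twice daily taVNS-paired feeding". Limitations confirms that there is no sham. The historical group consists of infants who received a G-tube, and the plan gives no method for comparing volume trends with theirs.

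Three places bear on the trend at entry:

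- Section A says that mastering oral feeding "typically takes 3-6 weeks of working on oral feedings in the hospital", for preterm and HIE infants alike.
- The inclusion criteria set the practice already completed: "If born premature have been working on oral feeding for 30days" for preterm infants, and for term infants "have been working on oral feeding for 14days". They also require that a G-tube is under discussion.
- Section E, Risks to the Subjects, says infants enter only if "not making progress with OT training, and are in discussion for Gtube placement".

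**The concern.** A comparison of epoch means estimates a difference in level. If an infant's intake was rising steadily before stimulation and goes on rising at the same pace, the treated epoch is higher than the baseline epoch although taVNS did nothing. With no control arm, nothing else in the volume analysis separates the two explanations. Leaving the epoch length open between 7 and 10 days adds to this: under a steady trend, the apparent gain grows with the epoch chosen.

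At stake is how a primary outcome is read in a study whose stated goal includes informing a decision on a larger randomised trial.

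**Working it through.** **No figure to reproduce.** The plan states no alpha, power, effect size or SD, and the sample size is not derived. What follows shows a range under stated assumptions.

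**Inputs.**
- From the documents: n = 40 (the maximum) and epochs of 7 or 10 days.
- Assumed: two-sided 5% test; one baseline epoch against the adjacent treated epoch; a constant residual slope through both; no taVNS effect; volume as a percentage of full intake; SD of the within-infant epoch difference from 10 to 40 points, held the same for both epoch lengths.

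**Formulas.** With two epochs, repeated measures ANOVA is a paired t-test.
- Spurious shift = slope × epoch length, because the midpoints of adjacent equal epochs lie one epoch length apart.
- Noncentrality = shift ÷ (SD ÷ √40), with √40 = 6.325.
- Rejection probability is from the noncentral t distribution on 39 degrees of freedom.

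**Slope zero.** The shift is 0 and the test rejects 5% of the time, whatever the SD.

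**Slope 0.5 points per day.** The shift is 7 × 0.5 = 3.5 points or 10 × 0.5 = 5.0 points.

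| SD of epoch difference | Standard error | Noncentrality, 7-day / 10-day | Rejection, 7-day / 10-day |
|---|---|---|---|
| 10 | 1.58 | 2.21 / 3.16 | 58% / 87% |
| 15 | 2.37 | 1.48 / 2.11 | 30% / 54% |
| 20 | 3.16 | 1.11 / 1.58 | 19% / 34% |
| 30 | 4.74 | 0.74 / 1.05 | 11% / 18% |
| 40 | 6.32 | 0.55 / 0.79 | 8% / 12% |

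**Epoch length.** At any non-zero constant slope the apparent gain with 10-day epochs is 10/7 = 1.43 times that with 7-day epochs. At zero slope the difference disappears.

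**Does a rate comparison remove the problem?** A simulation without a taVNS effect used linear infant trends (slope SD 1.5 points per day) and autocorrelated daily noise (SD 15, correlation 0.5), with 2,000 runs per scenario. At n = 40 the epoch-mean test rejected in about 5% of runs at zero mean slope, 10-12% at 0.24 points per day and 38-51% at 0.60 points per day. The before/after slope-change test rejected in 4-6% in every scenario. All these trends were linear, so the result says nothing about acceleration, a ceiling, or recovery from a low point.

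**The case against.** The strongest reply is that these infants are selected because they have stalled. If the statement in Risks to the Subjects is applied strictly, the trend at entry is close to flat and the epoch-mean test keeps roughly its nominal error. This stands as a limit on the size of the problem. It does not close it. The no-progress condition has no numerical definition and is missing from the inclusion list, which works by days of practice and G-tube discussion. Term infants may also enter after 14 days, inside the 21-42 days of the general course.

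A reader might go further and infer that a positive result is likely without any effect, because 3-6 weeks to full intake means 100/42 = 2.4 to 100/21 = 4.8 points per day. The documents do not support that. The course describes preterm and HIE infants in general, whereas the trial takes those who are failing it. The figures also do not fit a constant slope through treatment. On a linear 6-week course a preterm infant at 30 days would already be at 30/42 = 71% of intake, with 12 days left before the ceiling. On a 3-week course a term infant at 14 days would be at 14/21 = 67%, with 7 days left. Treatment lasts 14-21 days.

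It is also fair to say that the plan already names the better quantity, the rate of increase, and names it before the ANOVA. What is missing is its model and its priority.

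Finally, the end of section B ranks the improvement hypotheses below safety and feasibility, and the plan acknowledges the lack of a sham. That reduces the consequence. It does not change what the epoch-mean test measures, and volume change is still listed as a primary outcome.

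**Conclusion.** The concern holds as a bias of uncertain size. The epoch-mean ANOVA cannot tell a taVNS effect from a rise already under way, and nothing else in the design does so for volume. The false-positive rate is 5% if the trend at entry is flat. At an assumed 0.5 points per day it runs from 8% to 87% across SDs of 10 to 40 points and epochs of 7 to 10 days. The documents give neither the residual slope nor the SD, so they do not establish that a spurious positive is likely, only that the plan does not guard against one.

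This should be fixed before the volume data are analysed. It does not undermine the safety and feasibility aims.

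**What to change.** State in Data Analysis that the rate comparison is the deciding volume analysis. Fit it as a segmented mixed model on daily oral intake, with an infant-specific intercept and pre-treatment slope, and a step and a slope change at the first taVNS day, both reported with 95% confidence intervals. Fix the pre-treatment window in advance. Report epoch means descriptively at one fixed length, and say that a rise in epoch means alone is not evidence of effect.

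Also state what the model does not remove: late acceleration in feeding, regression to the mean after enrolment at a low point, and the ceiling at full feeds. The uncontrolled design therefore stays as a limitation.

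The cost is a change of wording. The primary outcome already requires daily volumes before and during treatment, and no extra infants or procedures are needed. The price is a wider interval than the epoch-mean difference would give.
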